#### **Statistical Analyses:**

There is no statistical hypothesis associated with the immunogenicity objective. All analyses will be run descriptively.

The primary objective is to evaluate the persistence of the antibody response against N. *meningitidis* serogroups A, C, W and Y at approximately 1 year after completion of a 4-dose infant vaccination. This persistence will be summarized as the percentage of subjects with a titer  $\geq 8$  (hSBA) or with a titer  $\geq 8$  and  $\geq 128$  (rSBA) along with associated two-sided 95% Clopper-Pearson confidence intervals.

The antibody titers will be summarized using GMTs with two-sided 95% confidence intervals constructed by exponentiation (base 10) of the means and confidence limits of the logarithmically transformed (base 10) antibody titer. Moreover the geometric mean ratios (GMR) between visit 6 (1 year after full vaccination) and visit 5 (1 month after full vaccination) will be provided along with the 2-sided 95% confidence intervals.

Approximately 135 subjects will be enrolled in this study providing approximately 100 evaluable subjects, assuming a 25% drop-out. The sample size is based on the number of subjects requested and agreed with South Korean Health Authorities for this persistence

Name of Sponsor:	Protocol number:	Generic name of study vaccine(s):
Novartis Pharma Services AG	V59_75	MenACWY-CRM (Menveo®) is a Meningococcal (Groups A, C, Y and W-135), Oligosaccharide Diphtheria CRM 197 Conjugate Vaccine.

study.

With 100 evaluable subjects, the 95% confidence limits of the observed percentages of subjects with hSBA titer  $\geq$ 8 or rSBA titer titer  $\geq$  8 or  $\geq$ 128 will be as presented in the following table.

Table 4: Calculated 95% Confidence Interval, Associated With Different Observed Percentages of Subjects

Observed percentage	95% confidence interval (Menveo® N=100)
50%	40%- 60%
60%	50%-70%
70%	61%-79%
80%	72%-88%
90%	84%-96%

Dependent on the point estimate, the length of the confidence interval will be 12% - 20%.

The analyses will be done on the Full Analysis Set (FAS population).

Additional details will be described in the statistical analysis plan.

### **Interim Analysis:**

The interim analysis is not applicable in this study.

# **Data Monitoring Committee:**

The Data Monitoring Committee is not Applicable for this study.

# **Time and Events Table – Treatment Period**

Visit Type		Clinic Visit	Phone Call	Clinic Visit	Phone Call	Clinic Visit	Phone Call	Clinic Visit	Phone Call	Clinic Visit	Clinic Visit
Study Day		1	3	61	63	121	123	301	304	331	661
Visit Window (Days)		n/a	-1/+1	+/-7	n/a	+/-7	-1/+1	+14	-1/+1	-7/+14	+/-60
Months of age		2		4		6		12		13	24
Visit Number		1		2		3		4		5	6
Study Event	References										
Study Treatment											
Vaccination	Section 5.2	X		X		X		X			
Screening and Safety											
Inform Consent *	Section 5.1.1	X a									
Medical History	Section 5.1.2	X									
Physical Exam	Section 5.1.2 and 5.3.1	X b		X		X		X	•	X	X
Exclusion/Inclusion Criteria	Section 4.0	X c		X		X		X		X	X
30 Minutes Post Injection Assessment	Section 5.2.1	X		X		X		X			
Subject Diary Dispensed/Training	Section 5.2.1	X		X		X		X			
Subject Diary Reminder Call	Section 5.2.2		X		X		X		X		
Subject Diary Review/ Collect	Section 5.3.1			X		X		X		X	
Assess all solicited AEs	Section 7.1.1 and 7.1.3	$X^d$		X d		X d		X d		$X^{d}$	

Confidential

Visit Type		Clinic Visit	Phone Call	Clinic Visit	Phone Call	Clinic Visit	Phone Call	Clinic Visit	Phone Call	Clinic Visit	Clinic Visit
Study Day		1	3	61	63	121	123	301	304	331	661
Visit Window (Days)	Visit Window (Days)		-1/+1	+/-7	n/a	+/-7	-1/+1	+14	-1/+1	-7/+14	+/-60
Months of age	Months of age			4		6		12		13	24
Visit Number		1		2		3		4		5	6
Study Event	References										
Assess SAEs	Section 7.1.4	Xe		Xe		Xe		X e		Xe	Xe
Medically attended AEs, AEs leading to withdrawal	Section 7.1.4.1 and 7.1.3			X c		X c		X c		Xe	Xe
Immunogenicity											
Serology blood draw	Section 3.5.									X	X

#### Notes:

- a. Confirm consent form(s) signed prior to any procedures. \* May be collected up to 5 days prior to vaccination on day 1.
- b. Physical examination must be performed by a qualified healthcare professional.
- c. Procedures to be performed prior to vaccination.
- d. Only solicited adverse event (AE) occurred during the day of each vaccination and for the following 6 days will be reported by the subject on a subject diary.
- e. SAEs, medically attended AE and AEs leading to study or vaccine withdrawal will be collected through Day 661. Please see section 6.6 for greater detail regarding methods for SAE and AEs leading to study or vaccine withdrawal collection

#### LIST OF ABBREVIATIONS

AE Adverse Event

BCDM Biostatistics and Clinical Data Management

BLA Biologic License Application

CI Confidence Interval

CRO Contract Research Organization

EC Ethics Committee

eCRF Electronic Case Report Form
EDC Electronic Data Capture
EDT Electronic Data Transfer
EMA European Medicines Agency

FAS Full Analysis Set

FDA Food and Drug Administration

GCP Good Clinical Practices
GMT Geometric Mean Titer

hSBA Human Complement Serum Bactericidal Assay rSBA Rabbit Complement Serum Bactericidal Assay

IB Investigator's Brochure ICF Informed Consent Form

ICH International Conference on Harmonisation of Technical

Requirements for Registration of Pharmaceuticals for Human Use

IM Intramuscular

IRB Institutional Review Board

MedDRA Medical Dictionary for Regulatory Activities

MFDS Ministry of Food Drugs and Safety

PP Per Protocol

Doc Number: 68901057

SAE Serious Adverse Event SDA Source Data Agreement SOP Standard Operating Procedure

TV Termination visit

#### 1.0 BACKGROUND AND RATIONALE

### 1.1 Background

Meningococcal disease is caused by a gram-negative diplococcus, *Neisseria meningitidis*. Invasive infection by *N. meningitidis* usually results in bacteremia and/or meningitis, and can be complicated by purpuric rash (meningococcemia), arthritis, myocarditis, pericarditis, endophthalmitis, or pneumonia. This disease often cannot be distinguished clinically from other forms of acute bacterial meningitis and sepsis caused by *Haemophilus influenzae* or *Streptococcus pneumoniae*. The signs of meningococcal meningitis in adults include headache, stiff neck, fever, chills, malaise, and prostration. Asymptomatic colonization of the upper respiratory tract by encapsulated *N. meningitidis* is common, yet only a small percentage of colonized persons develop disease. Transmission is thought to be via droplets of respiratory tract secretions.

Novartis Vaccines and Diagnostics has developed a quadrivalent conjugate vaccine aimed at preventing disease in infants and older age groups due to *Neisseria meningitidis* serogroups A, C, W, and Y. Serogroup prevalence varies with geography, time of year, and age group. Currently, serogroup B and C strains are most prevalent in Europe, and serogroup B, C and Y strains are most prevalent in North America.1

*N meningitidis* serogroup A strains are responsible for large epidemics of bacteremia and meningitis in sub-Saharan Africa, with attack rates as high as 500 to 1000 per 100,000 population.2 Outbreaks due to serogroup W have also recently been reported in the same geographic location and among Hajj pilgrims.

Meningococcal vaccines containing polysaccharides of serogroups A, C, W and Y were licensed to control meningococcal epidemics, but their use is limited by poor immune response and protection for young children, especially those younger than 2 years of age (the group that is generally at highest risk of disease). The available polysaccharide vaccines also do not induce immunologic memory and may trigger immunologic hypo responsiveness, even in older individuals.

Novartis' meningococcal C conjugate vaccine (Men C, Menjugate), has been licensed in over 30 countries worldwide and has been successfully used in immunization campaigns in response to serogroup C meningococcal outbreaks in the United Kingdom and Quebec, Canada (Trotter C, Lancet 2004: 364: 365-367). 12 The development program for Novartis' Meningococcal ACWY conjugate vaccine (Novartis MenACWY, Menveo®) builds upon this experience and includes manufacturing methods similar to those employed for Menjugate. In brief, the vaccine synthesis involves production of sized oligosaccharides from each of the four meningococcal serogroups (A, C, W, and Y) and their individual conjugation to the protein carrier, CRM197. Therefore, the intent of this

Doc Number: 68901057

program is to provide a meningococcal conjugate vaccine with broad serogroup coverage, protecting persons across all age groups, from infants through adults.

In 2010, Menveo®, (Meningococcal ACWY Conjugate Vaccine) was licensed for use in adolescents and adults, 11 years of age and older in the United States.

On October 27, 2010, the Advisory Committee on Immunization Practices (ACIP) approved updated recommendations for the use of quadrivalent meningococcal conjugate vaccines in adolescents and persons at high risk for meningococcal disease (Recommendations of the Advisory Committee on Immunization Practices (ACIP). Morbidity and Mortality Weekly Report (MMWR). The two new recommendations approved are: (1) a booster dose at age 16 years in subjects immunized at 11 to 12 years of age and (2) a 2-dose primary series administered 2 months apart for persons aged 2 through 54 years with persistent complement component deficiency (e.g., C5--C9, properidin, factor H, or factor D) and functional or anatomic asplenia, and for adolescents with human immunodeficiency virus (HIV) infection.

Supplementary BLAs (sBLAs) for an expanded age indication in children (2 10 years of age) and infants (2-23 months of age) were approved in US in January 2011 and August 2013, respectively. In EU two variations for the same extensions were submitted in August 2011. The variation to expand age indication in children (2-10 years of age) was approved in April 2012. Currently MenACWY vaccine is registered for vaccination of adolescents and adults in more than 60 countries; many of these countries have also approved use in children (2 10 years of age) and infants (2-23 months of age).

#### 1.2 Rationale

Novartis MenACWY (Menveo®) has been approved for use in people 2 months through 55 years of age in the United State and in people of 2 years and above in Europe and other countries, including the Republic of South Korea. In South Korea, the indication was extended in May 2014 to infants 2 months of age to 55 years, and as post commitment of indication change, the Regulatory Authorities of the Republic of South Korea, (MFDS) have requested data on immunogenicity persistence in the Korean children who received 4 doses of Menveo® at 2-4-6-12 months of age.

#### 2.0 **OBJECTIVES**

## 2.1 Primary Objective(s)

## **Primary Safety Objective(s)**

To assess the safety and tolerability of MenACWY administered at 2-4-6 and 12 months of age.

### **Primary Immunogenicity Objective(s)**

- 1. To evaluate the persistence of the antibody response against *N. meningitidis* serogroups A, C, W and Y at approximately 1 year after completion of a 4-dose infant vaccination series (2, 4, 6 and 12 months of age) of MenACWY vaccine as measured by hSBA titers ≥8.
- 2. To evaluate the persistence of the antibody response against *N. meningitidis* serogroups A, C, W and Y at approximately 1 year after completion of a 4-dose infant vaccination series (2, 4, 6 and 12 months of age) of MenACWY vaccine as measured by rSBA titers ≥8 and ≥128.

# 2.1 Secondary Objective(s)

### **Secondary Immunogenicity Objectives**

- 1. To describe hSBA titers ≥8 and hSBA GMTs against *N. meningitidis* serogroups A, C, W and Y 1 month after a full vaccination series at 2,4,6 and 12 months of age
- 2. To describe rSBA titers ≥8 and ≥128 rSBA and GMTs against *N. meningitidis* serogroups A, C, W and Y 1 month after a full vaccination series at 2,4,6 and 12 months of age
- 3. To evaluate the persistence of the antibody response against *N. meningitidis* serogroups A, C, W and Y at approximately 1 year after completion of a 4-dose infant vaccination series (2, 4, 6 and 12 months of age) of MenACWY vaccine as measured by hSBA GMTs and rSBA GMTs

#### 3.0 STUDY DESIGN

# 3.1 Overview of Study Design

This is a Phase IV multicenter open label, post marketing committement study to evaluate the persistence of antibody response in approximately 135 children 1 year after completion of series of Menveo® vaccination at 2-4-6-12 month vaccination. The study foresees 6 clinical visits, 2 blood draws (at 13 and 24 months) and 4 reminder phone calls. The subjects study participation is approximately 22 months.

Table 3.1-1 Overview of the study design

N Subjects	Visit 1	Visit 2	Visit 3	Visit 4	Visit 5	Visit 6
N Subjects	2-Months	4-Months	6-Months	12-Months	13- Months	24- Months
135	Menveo®	Menveo®	Menveo®	Menveo®	Blood draw	Blood draw

The informed consent will be obtained prior to any study-related procedures and subjects will be enrolled only after their eligibility for participation is confirmed by the investigator. All participants will receive 4 doses of Menveo® in an open label fashion. A total of two blood samples will be drawn from all subjects for immunogenicity evaluation at the following time points: 1 month after the fourth and last dose of Menveo® vaccine, (Visit 5, 13 months of age) and one during the last clinical visit (Visit 6, 24 months of age).

After each vaccination, all subjects will remain under medical supervision at the study site for at least 30 minutes to be monitored in case of a hypersensitivity reaction. Furthermore, subject's parent/legal guardian will be instructed on the completion of a subject diary, to record solicited local and systemic AEs and other solicited events (including body temperature and use of analgesics/antipyretics for prophylaxis or treatment), for 7 days, starting on the day of vaccination and continuing during each of the 6 days following vaccination. They will also be instructed to call the site if they develop any adverse event(s) of concern including those which require admission to a hospital or an emergency room or a visit to/by a doctor. In order to ensure proper completion of the subject diary four reminder calls will be carried out by the site staff 2 days after each vaccination visit (e.g. on Day 3).

Subject diary will be collected by study staff at the next clinical study visits until visit 5. The safety information obtained by study personnel will be recorded on the appropriate web based system referred to as Electronic Data Capture (EDC).

Site staff will record the following selected safety measures in the EDC:

- Solicited local adverse events: Injection site erythema, injection site induration, injection site tenderness (from Day 1 to Day 7 after each Men ACWY vaccination)
- Solicited systemic adverse events: Change in eating habits, sleepiness, irritability, vomiting, diarrhea, fever (from Day 1 to Day 7 after each Men ACWY vaccination).
- Unsolicited Adverse Events: All medically-attended unsolicited AEs and AEs leading to premature withdrawal will be collected (From Day 1 of the study and orally during the last clinical visit)
- Serious AEs: All SAEs will be collected from day 1 to end of study. SAEs will be
  monitored until resolution and/or the cause is identified (if a SAE remains
  unresolved at study termination, a clinical assessment will be made by the
  investigator and the Novartis medical monitor to determine whether continued
  follow up of the SAE is warranted) Medications used to treat any medicallyattended AE and SAE will be collected from Day 1 of the study and during the
  last clinical visit
- Note that all medically-attended unsolicited AEs, AEs leading to premature withdraw and all the medication used to treat them, these data will be captured by interviewing the subject and/or subjects' parents/guardian (as applicable) during clinic visits.

### 3.2 Study Period

Each subject should expect to participate in the study for 22 months, from the time of enrolment through the last study visit.

# 3.3 Blinding Procedures

The trial is designed as an open label study; therefore blinding procedures are not applicable.

### 3.4 Data Collection

### 3.4.1 Data Collected from Subjects

The following data will be collected from each subject over the duration of their study participation:

• Demographic Information (Date of Birth, Sex, Weight, Height)

- Adverse Events Seriousness, Date of Onset, Date of Resolution, Frequency, Severity, Actions Taken, Outcome, Relationship to Study Vaccine
- Medical History that may be relevant to subject eligibility for study participation such as prior vaccinations
- Concomitant Medications
- Vaccination record (Pre-Vaccination Body Temperature, Date of Vaccination, Injection Site)
- Study termination (Reason(s) for ending study participation or Reason(s) for early termination)

All data collected must only be identified using the Novartis Subject ID, as described in section 5.1.4, Randomization.

#### 3.4.2 Tools Used for Data Collection

Data will be recorded in the Subject Diary and collected on Case Report Forms (CRFs).

### **Subject Diary**

Paper Diaries (pDiaries) hereafter referred to as Subject Diaries will be the only source document allowed for solicited local and systemic adverse events (including body temperature measurements), starting after the initial 30 minute post-vaccination period at the clinic. The following additional rules apply to documentation of safety information collected in the Subject Diary.

- 1. No corrections or additions to the information recorded by the subject within the Subject Diary will be allowed after it is delivered to the site.
- 2. Any blank or illegible fields on the Subject Diary must be described as missing in the CRF.

### Case Report Forms

This study utilizes Case Report Forms (CRFs) to collect study-related data from each subject. A qualified site staff member(s) is required to enter subject data in the CRFs in English based on the medical information available in each subject's source record.

Data should be entered into the CRF in a timely fashion following each subject's clinic visit, study procedure, or phone call. Each subject's CRF casebook will be compared with the subject's source records by a Novartis-approved study monitor (or designee) over the duration of the study in order to ensure data collection accuracy.

PRO-01 TEMP 06 / Atlas No. 293620 Version No. 3 / Version Date: November 10, 2014 The following additional rules apply to documentation of Subject Diary information collected in the CRFs:

- 1. The site must enter all readable entries in the Subject Diary into the CRF, including those values that may be biologically implausible (e.g. body temperature: 400°C).
- 2. Any illegible or implausible data should be reviewed with the parent(s)/legal guardian(s). If an underlying solicited or unsolicited adverse event is described on review with the subject, this should be described in the source document and reported as an unsolicited adverse event in the Adverse Event CRF (e.g., if the subject above confirms body temperature of 40°C on the day in which body temperature: 400°C was written into his/her Subject Diary, this fever of 40°C should be recorded in the Adverse Event CRF).
- 3. Any newly described safety information (including a solicited adverse event) must not be written into the Subject Diary and must be described in the study file as a verbally reported adverse event. Any adverse event reported in this fashion must be described as an unsolicited adverse event and therefore entered on the Adverse Event CRF.

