#### 8.4.2.1.2 Analysis of Solicited Local, Systemic and Other Adverse Events

Most solicited adverse events will be summarized according to defined severity grading scales

Frequencies and percentages of subjects experiencing each adverse event will be presented for each symptom severity. Summary tables showing the occurrence of any local or systemic adverse event overall and at each time point will also be presented.

Post-vaccination solicited adverse events reported from 30 minutes, Day 1 to Day 3, Day 4 to Day 7 and Day 1 to Day 7 will be summarized by maximal severity.

The severity of solicited local adverse events, including injection site erythema, injection site induration, injection site tenderness will be categorized as none, 1 to  $\leq$ 25 mm, 26 to  $\leq$ 50 mm, and  $\geq$ 50 mm (severe local reactions).

Injection site pain/tenderness and systemic adverse events (except fever) occurring up to 7 days after each vaccination will be summarized according to "mild", "moderate" or "severe".

Each solicited local and systemic adverse event will also be further summarized as "none" versus "any".

Implausible measurements (for further definition see statistical analysis plan) will be left out of the analysis.

Use of antipyretics and analgesics will be summarized by frequency by type of use (prophylactic versus treatment) and percentage of subjects reporting use. The influence of antipyretics and analgesics use on the occurrence of specific adverse events (e.g., fever, pain) will be assessed.

Body temperature will be categorized as  $<38^{\circ}$ C (no fever),  $38-38.9^{\circ}$ C (Mild),  $39-39.9^{\circ}$ C (Moderate), and  $\ge 40^{\circ}$ C (severe). Body temperature will also be summarized by  $<38^{\circ}$ C (no fever),  $38-38.4^{\circ}$ C,  $38.5-38.9^{\circ}$ C,  $39-39.4^{\circ}$ C,  $39.5-39.9^{\circ}$ C, and  $\ge 40^{\circ}$ C (severe).

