# **6.3** Exclusions of Individual Values for Safety Analysis

Some local and systemic adverse events will be directly measured by the subject and will not be subject to a reconciliation process, even if they are biologically implausible. Therefore these implausible measurements will be removed from the analysis but included in listings. Implausible measurements are summarized in the table below:

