# 13.2 Solicited Local and Systemic Adverse Events

For details please refer to section 7.1.1 of the protocol.

Only solicited local and systemic adverse events reported in the diary card will be analyzed. Implausible measurements will not be taken into consideration in the analysis but listed in the Appendix (see section 6.3). An overview of the collected solicited adverse events with severity indication is presented in Table 13.1.

Table 13.2-1: Overview of the Solicited Adverse Events with Severity Grading

	Reaction	Grade 0/None	Grade 1/Mild	Grade 2/Moderate	Grade 3/Severe
	Erythema	<10 mm	10-25 mm	26-50 mm	>50 mm
ਕ	Induration	<10 mm	10-25 mm	26-50 mm	>50 mm
Local	Tenderness	None	Minor light reaction to touch	Cried or protested to touch	Cried when injected limb was moved
	Change in eating habits	None	Eating less than normal for 1 - 2 feeds / meals	Missed 1 or 2 feeds / meals	Missed more than 2 feeds / meals
	Sleepiness	None	Shows an increased drowsiness	Sleeps through feeds / meals	Sleeps most of the time and it is hard to arouse him / her
Systemic	Irritability None		Requires more cuddling and is less playful than usual	More difficult to settle	Unable to console
S	Vomiting	None	1 - 2 times in 24 hours	3 - 5 times in 24 hours	6 or more times in 24 hours or requires intravenous hydration
	Diarrhea Fewer than 2 loose stools in 24 hours		2 - 3 loose stools in 24 hours	4 - 5 loose stools in 24 hours	6 or more loose stools in 24 hours or requires intravenous hydration
	Fever		Captured as No	o (<38°C) or Yes (≥38°C	)

Solicited adverse events will be reported at 30 minutes, at 6 hours on day 1 and then daily until day 7 using structured diaries. The analyses of solicited adverse events will be done separately for 30 minutes and based on three intervals: 6h - day 3, day 4 - day 7 and 6h - day 7, each without 30minutes data. In addition solicited adverse events ongoing after day 7 will be presented as unsolicited AE.

Doc Number: 80333235

For erythema and induration, recorded originally as diameters (mm), the following categorizations will be used to summarize the data for a pediatric population:

Type I: none (0 mm), any (1-9 mm, 10-25 mm, 26-50 mm, >50 mm)

Type II: Grade 0 (< 10 mm), any (10-25 mm, 26-50 mm, >50 mm)

Body temperature will be broken down by route of measurement according to the recommendations of the Brighton collaboration and will be summarized according to the 3 schemes described below:

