- by 0.5 °C increments: <36.0, ≥36.0-<36.5, ≥36.5-<37.0, ≥37.0-<37.5, ≥37.5-<38.0, ≥38.0-<38.5, ≥38.5-<39.0, ≥39.0-<39.5, ≥39.5-<40.0, ≥40.0°C
- by 1.0 °C increments: <36.0, ≥36.0-<37.0, ≥37.0-<38.0, ≥38.0-<39.0, ≥39.0-<40, ≥40°C
- $<38.0, \ge38.0$  °C

Fever, defined as a body temperature of  $\ge 38^{\circ}$ C irrespective of route of measurement, will be integrated to the summaries as an indicator of a systemic adverse event.

The analyses will encompass summaries of the data on five levels:

- 1. Daily reports of subjects with solicited adverse events.
- 2. Time of first onset of solicited adverse events (excluding 30 min measurement).
- 3. Solicited adverse events, maximum event severity by event and interval (6h day 3, day 4 day 7, and 6h day 7, each without 30 min).
- 4 Duration of solicited adverse events
- 5. Solicited adverse events and indicators of solicited adverse events, occurrence of at least one event by category (local, systemic) and interval 6h-day 3, day 4- day 7 and 6h-day 7, each without 30 min.

For each of the time points or time intervals presented in the summaries, only subjects with at least one plausible observation (i.e., any non-missing values but excluding "Not done/unknown" and implausible values) for the solicited adverse events in the interval of interest will be considered. Subjects without plausible data (i.e. missing values or reported as "Not done/unknown" and implausible values) will be removed from the denominator to prevent a downward bias (towards zero).

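### Solicited events confirmed by the parent at diary review are filed as unsolicited and so are missing from the solicited safety analysis, whose rates can then only fall or stay the same

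*Protocol*

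**What the plan says.** Protocol 3.4.2 (Subject Diary) closes the diary once it is handed over: "No corrections or additions to the information recorded by the subject within the Subject Diary will be allowed after it is delivered to the site". It adds: "Any blank or illegible fields on the Subject Diary must be described as missing in the CRF".

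Protocol 3.4.2 (Case Report Forms) has three rules. Rule 1: readable entries go into the CRF as written, even when impossible. Rule 2: illegible or implausible entries are reviewed with the parent, and an event described at that review is "reported as an unsolicited adverse event in the Adverse Event CRF". In the protocol's example, 400°C in the diary is confirmed as 40°C and "this fever of 40°C should be recorded in the Adverse Event CRF". Rule 3: safety information first described verbally, including a solicited event, is handled the same way.

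On analysis, Protocol 8.4.2.1.2 says: "Implausible measurements (for further definition see statistical analysis plan) will be left out of the analysis". SAP Table 6.3-1 sets the temperature limits at 33°C or below and 42°C or above. SAP 13.2 says: "Only solicited local and systemic adverse events reported in the diary card will be analyzed". For each time point or interval it considers "only subjects with at least one plausible observation", and a child with none is taken out of the denominator. Level 3 then takes the maximum severity over what remains.

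Protocol 8.1.1.1 places solicited events on Days 1 to 7, including fever of 38°C or more, in the primary safety endpoint. The changes listed for the protocol amendments and for SAP version 2 do not touch these rules.

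**The concern.** Each rule is reasonable alone. Together they remove from the solicited tables an event that the study has established. The diary value is deleted as implausible or coded missing, the confirmed value sits on a form that the solicited analysis does not read, and the child may be scored on the remaining days as if nothing had happened.

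SAP 13.2 explains its denominator rule as protection against bias towards zero. That protection suits values that are unknown. Here the value is known to be an event, so neither keeping the child on the other readings nor removing the child prevents the bias. The most exposed figures are the rare, high categories such as 40°C or more, where one child is a large share of the count.

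**Working it through.** **No plan figure to reproduce.** The documents give no frequency for such entries. The check applies the SAP rules to example diaries and then scales the effect.

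**Rules applied** (SAP 6.3, Table 6.3-1, SAP 13.2): drop readings of 33°C or below, 42°C or above, or missing; require at least one remaining reading; take the maximum; fever if it is 38°C or more. There are seven time points (6 h, days 2 to 7). The event falls on day 3, written as 400°C and confirmed as 40°C. The other temperatures are assumptions.

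| Example | 6h-day 3 | 6h-day 7 | Day 3 daily table |
|---|---|---|---|
| A. All other readings plausible and below 38°C | no fever | no fever | removed |
| B. Day 2 is 38.6°C, day 4 is 38.2°C | fever, highest 38.6°C | fever, highest 38.6°C | removed |
| C. No other plausible reading | removed | removed | removed |
| D. Plausible readings on days 4-7 only, all below 38°C | removed | no fever | removed |
| E. As A, but the entry is illegible | no fever | no fever | removed |

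The child is scored as no fever in A and E, and in D for 6h-day 7. In B the child still counts as fever, but in the 38.5 to below 39.0°C band instead of 40°C or more. In C the child leaves the denominator.

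**Effect on the any-fever rate.** Let n be the denominator and x the true number with fever. I use n = 135 (enrolled) and n = 100 (the planned evaluable number) as an assumed range, because per-dose safety denominators are not stated.

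- Child scored as no fever: the rate falls by 1/n. 1/135 = 0.74 points; 1/100 = 1.00 point. For k such children the fall is k/n: at n = 135, k = 1 to 5 gives 0.74 to 3.70 points.
- Child removed: the rate falls by x/n − (x−1)/(n−1) = (n−x)/[n(n−1)]. For assumed fever rates of about 5% and 20%:
  - n = 135, x = 7: 5.19% becomes 6/134 = 4.48%, a fall of 0.71
  - n = 135, x = 27: 20.00% becomes 26/134 = 19.40%, a fall of 0.60
  - n = 100, x = 5: 5.00% becomes 4/99 = 4.04%, a fall of 0.96
  - n = 100, x = 20: 20.00% becomes 19/99 = 19.19%, a fall of 0.81
- Child with another diary fever: no change.

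Since x is never above n, (n−x)/[n(n−1)] is never negative. A confirmed fever left out of the analysis therefore cannot raise the any-fever rate. A lower band can gain a child, as in B, but no rate at or above a threshold rises.

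**Effect on the 40°C-or-more category.** Assume two true events among 135: 2/135 = 1.48%. If one was miswritten, the table shows 1/135 = 0.74% (A, B, D or E) or 1/134 = 0.75% (C), about half. The event drops out of this category in all five examples.

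**The case against.** **Always scored as no fever.** A reader might infer that every such child is tabulated this way. The documents do not support that: SAP 13.2 removes a child with no plausible reading in the interval, and a fever on another diary day still counts. In the daily table for the affected day the child is removed, never scored as none.

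**Event lost.** A reader might infer that the event vanishes from the report. It does not. Protocol 8.4.2.1.3 summarises all reported adverse events by system organ class and preferred term and lists them by subject. SAP 13.3 describes preferred-term frequency tables, SAP 13.4 gives a combined solicited and unsolicited summary, and implausible values are listed. Two limits remain. The eight categories itemised in SAP 13.3 have no line for a non-serious fever managed at home without effect on participation or dosing. SAP 13.4 also says its combined summary cannot be split by severity.

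**SAP 6.3 against the protocol.** SAP 6.3 says such measurements "will not be subject to a reconciliation process, even if they are biologically implausible", which might seem to contradict the rule 2 review. It does not: that review creates a separate adverse event record and never amends the diary measurement.

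**Diary-only by design.** The diary is the declared sole source for solicited events. It is reviewed at the next visit, about 60 days after doses 1 and 2, 180 days after dose 3 and 30 days after dose 4. Keeping recalled events apart from same-day entries is defensible, and this stands as a reason not to replace the diary-only figure.

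**Small and descriptive.** The study has one arm and no success criteria, so no decision depends on this count. Implausibility limits exist only for temperature, erythema and induration; other solicited events are affected only through illegible entries or rule 3. Both points limit the importance. Neither removes the direction of the bias.

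**Conclusion.** The concern holds in a conditional form. A solicited event confirmed under rules 2 or 3 of Protocol 3.4.2 is absent from the solicited analysis. What happens to the child depends on the other readings in the interval: scored as none, removed, or counted at a lower category.

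The any-event rate falls or is unchanged. Per affected child the fall is 0.74 points when scored as none and 0.60 to 0.71 when removed at n = 135, or 1.00 and 0.81 to 0.96 at n = 100. The removal figures assume true rates of 20% down to 5%. The total effect cannot be stated, because the number of such children is not given. The halving at 40°C or more illustrates two assumed events, one of them miswritten; it is not a forecast.

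This bears on the accuracy of a primary descriptive safety endpoint, not on any test or decision. It is worth correcting because the data are already collected and the SAP itself aims to avoid bias in this direction.

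**What to change.** Keep the diary-only analysis as primary. In SAP 13.2 add a supplementary count beside it:

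- At Level 5 (any versus none), include adverse event CRF records on solicited terms with onset on Days 1-7 after a dose, reported under rules 2 or 3 of Protocol 3.4.2.
- In the temperature categories, include the confirmed temperature where one is recorded.
- State how many such events there are, by dose.

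Do not carry CRF severity into the Level 3 grades for other events. Protocol 7.1.3 grades by limitation of daily activity, whereas SAP Table 13.2-1 uses event-specific scales such as missed feeds, loose stools or millimetres, and there is no mapping between them. SAP 6.3 needs no change on this account.

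The cost is SAP wording and one derivation, with no new data collection. The downside is that the added events rest on recall at the next visit, about 60 to 180 days later for doses 1 to 3. They should therefore stand beside the diary-only figures, not in place of them.
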